1.0 Objectives

1.1 Study Objectives

Describe the purpose, specific aims or objectives. State the hypotheses to be tested.

This pilot study seeks to determine if formula feeding recommendations that are calibrated using age and weight specific caloric intake recommendations can prevent excessive infant weight gain and reduce overweight in the first 6 months after birth among infants born to mothers with overweight prior to pregnancy electing to exclusively formula feed their infants. Calibrated formula feeding refers to adjusting the recommended daily caloric formula intake to account for weight status. A cohort of 60 infants will be recruited and randomized 2-3 weeks after birth to an intervention arm characterized by calibrated formula feeding recommendations or a control group with ad lib feeds as per usual care. Intervention group parents will also be given written instructions on infant hunger and satiety cues as well as copies of videos with guidance on bottle feeding and how to soothe fussy infants without feeding. We hypothesize that the calibrated formula intake intervention will reduce rapid infant gain and overweight during infancy resulting in lower weight-for-length at age 6 months.

1.2 Primary Study Endpoints

State the primary endpoints to be measured in the study.

Clinical trials typically have a primary objective or endpoint. Additional objectives and endpoints are secondary. The endpoints (or outcomes), determined for each study subject, are the quantitative measurements required by the objectives. Measuring the selected endpoints is the goal of a trial (examples: response rate and survival).

- Conditional Weight Gain between Birth and Age 6 months

1.3 Secondary Study Endpoints

State the secondary endpoints to be measured in the study.

- Conditional Weight Gain during the intervention period spanning Ages 1-6 Months
- Mean Weight-for-Length Z-score (WLZ) at Age 6 Months
- Growth Trajectory during the intervention period spanning Ages 1-6 Months (repeated measures of weight-for-length)
- Proportion of Infants with Overweight (Weight-for-Length $\geq 95^{\text{th}}$ Percentile on WHO Growth Charts) at Age 6 months
- Feasibility: a) recruitment, b) ability to give tailored formula volume recommendations, c) visit completion, d) retention through 6 months
- Acceptability: parent adherence to formula volume recommendations as measured by 3 day feeding diaries at 2, 3, 4, 5, and 6 months for the intervention group

2.0 Background

2.1 Scientific Background and Gaps

Describe the scientific background and gaps in current knowledge.

For clinical research studies being conducted at Penn State Health/Penn State College of Medicine, and for other non-PSH locations as applicable, describe the treatment/procedure that is considered standard of care (i.e., indicate how patients would be treated in non-investigational setting); and if applicable, indicate if the study procedure is available to patient without taking part in the study.

Infant obesity predicts childhood and adult obesity,¹⁻⁶ as the highest quintile of weight gain between birth and 5 months of age doubles the odds of overweight at 4.5 years.¹ Although familial lifestyle and environmental factors may contribute to the epidemic,⁷⁻⁹ we propose that developmental programming effects of the maternal environment during in utero and newborn periods result in early onset and persistent overweight/obesity (OW/OB).

What are the mechanisms that account for this generational cycle of OB and critical fetal/newborn periods? Increased *energy intake*, not reduced energy expenditure, largely explains population weight gain in children and adults.¹⁰⁻¹³ Even a small mismatch (<0.5%) in intake/expenditure will lead to weight gain over time.¹⁴ Thus, the combination of appetite/satiety and the energy content of foods represent a critical regulator of energy intake and OB in both adults and infants. As described below, we propose that programmed offspring hyperphagia combined with feeding of high caloric value breast milk or infant formula potentiates early life accelerated weight gain and the cycle of OW/OB.

Programmed Offspring Hyperphagia: During pregnancy maternal OW/OB impacts fetal brain development leading to a diversity of offspring neurodevelopmental disorders (e.g., cognitive, neurodegenerative)¹⁵⁻¹⁷ among which hyperphagia-induced OB may be the most recognizable. Maternal body mass index (BMI) is correlated with fetal and infant weight gain. Mothers with OW/OB have an increased risk of large for gestational age (LGA) newborns,¹⁸ which have a >2-fold risk of preschool OB¹⁹ and adult metabolic syndrome.²⁰⁻²⁸ The importance of the pregnancy environment is evidenced by the finding that children of mothers with OB who have undergone bariatric surgery are three-times less likely to be severely obese when compared to siblings born prior to surgery.²⁹ Furthermore, the critical role of maternal OW/OB is evidenced by the finding that paternal OB is associated with a four-fold increased risk of OB in daughters at age 18 years, while maternal OB results in an eight-fold increased risk.⁹

Animal studies have replicated evidence of human programmed obesity. In mice, offspring of OB, high fat diet rodents are predisposed to newborn OW and adult OB,^{30,31} and a spectrum of neurologic disorders.³²⁻³⁵ Within the hypothalamus, the maternal OW/OB nutritional environment alters neural cellular and epigenetic signaling that result in increased appetite and reduced satiety gene expression and neurons. Laboratory studies have demonstrated that maternal OB (and high fat diet) increases offspring hypothalamic neuronal peptides and orexigenic neurons,³⁶⁻³⁹ and programs offspring hyperphagia.^{30,36,40-43} Maternal OB reduces offspring pro-opiomelanocortin (POMC) expression with an increase in arcuate neuropeptide Y (NPY) signaling,⁴⁴ while offspring born to dams fed a high-carbohydrate diet demonstrate increased NPY release.⁴⁵ In rodents, offspring of obese dams exhibit decreased hypothalamic tissue expression of select neurogenic signal factors (Ngn3 and Mash1) which regulate neural progenitor cell differentiation to appetite vs satiety neurons, consistent with increased arcuate agouti-related peptide (AgRP) and reduced POMC expression.^{36,46} Maternal OB reduces offspring Mash1 mRNA expression and increases NPY neurons.³⁸ With evidence of programmed neurogenesis and hyperphagia, OW/OB LGA human and mouse offspring gain weight more rapidly than appropriate for gestational age (AGA) offspring.

What can be done: Despite these findings, effective interventions short of bariatric surgery to break the generational cycle of OB are limited to those promoting responsive parenting behavioral interventions.^{47,48} Although maternal lifestyle interventions and exclusive breastfeeding are optimal for many reasons, reports suggest limited efficacy at preventing obesity among offspring. Randomized studies have attempted pre-pregnancy weight loss or controlled gestational weight gain, also with limited effects on neonatal body composition.⁴⁹⁻⁵² Although neonatal care has incorporated nutrient fortification to preterm, low birth weight newborns to augment weight gain,⁵³ there have been no studies calibrating intake to prevent excess weight gain among term newborns at risk of OW/OB.

We propose several discrete benefits of calibrated formula feeding recommendations that are age and weight-status specific to promote healthy newborn growth. The prevention of OW infants at 6 months of age would be predicted to reduce the rate of childhood and even adult OB. This may occur, in part, by preventing OB-associated leptin resistance. Thus, preventing the onset of infant OB,

hyperleptinemia and leptin resistance⁵⁴⁻⁵⁷ may normalize appetite throughout childhood. Further, consistent with evidence in animal models, calibrated intake and newborn growth may potentially reprogram the newborn hypothalamic arcuate nucleus, correcting the appetite/satiety neuronal ratio.⁵⁸ ⁶¹ In this project, we will examine the potential efficacy of a novel preventive strategy to normalize infant weight gain to prevent the development of infant OW and interrupt the cycle of OB.

2.2 Previous Data

Describe any relevant preliminary data.

N/A

2.3 Study Rationale

Provide the scientific rationale for the research.

Infancy is a critical period of developmental plasticity with lasting metabolic and behavioral consequences.⁶² Obesity is an outcome that is affected by this plasticity during infancy. The obesity epidemic is a public health crisis that will severely impact US children across their lifecourse and place a substantial burden on our healthcare system. Nearly 1 in 5 US children aged 2-19 are obese, and ~1 in 3 are overweight (BMIs $\geq 95^{\text{th}}$ and 85^{th} percentiles, respectively).^{63,64} For many children, this problem begins early as 23% of 2-5 years olds are already overweight⁶⁴ and 9-14% are already obese.^{63,65} Primary prevention is likely the best solution, as recent simulation data in the *New England Journal of Medicine* suggest that “a 2 year old who is obese is more likely to be obese at 35 years of age than an overweight 19 year old.”⁶⁶

Though somewhat controversial, there is evidence that formula feeding is associated with a modestly increased risk obesity⁶⁷⁻⁷¹ and rapid infant weight gain,⁷² with further evidence that the volume of formula consumed, overfeeding, an important contributor to excess weight gain^{73,74} as might be expected. Similar findings have been reported for bottle feeding.⁷⁵ Adjusting or calibrating the recommended amount of formula across the first 6 months after birth shows promise as a strategy to reduce rapid infant weight gain and early life overweight.⁷⁴

3.0 Inclusion and Exclusion Criteria

Create a numbered list below in sections 3.1 and 3.2 of criteria subjects must meet to be eligible for study enrollment (e.g., age, gender, diagnosis, etc.).

Vulnerable Populations:

Indicate specifically whether you will include any of the following vulnerable populations in this research. You MAY NOT include members of these populations as subjects in your research unless you indicate this in your inclusion criteria because specific regulations apply to studies that involve vulnerable populations.

The checklists referenced below outline the determinations to be made by the IRB when reviewing research involving these populations. Review the checklists as these will help to inform your responses throughout the remainder of the protocol.

- **Children** –Review “HRP-416- Checklist - Children”
- **Pregnant Women** – Review “HRP-412- Checklist - Pregnant Women”
- **Cognitively Impaired Adults**- Review “HRP-417- Checklist - Cognitively Impaired Adults”
- **Prisoners**- Review “HRP-415- Checklist - Prisoners”
- **Neonates of uncertain viability or non-viable neonates**- Review “HRP-413- Checklist - Non-Viable Neonates” or “HRP-414- Checklist - Neonates of Uncertain Viability”

[Do not type here]

3.1 Inclusion Criteria

Create a numbered list of the inclusion criteria that define who will be included in your final study sample (e.g., age, gender, condition, etc.)

1. Term or Early Term (≥ 37 weeks), singleton infants
2. Infant birthweight $\geq 50^{\text{th}}$ percentile based on the 2013 Fenton Growth Charts (which account for sex of child and gestational age at birth)
3. Infant without substantial neonatal morbidity that would affect feeding or weight gain (e.g. known chromosomal abnormality, metabolic disorder, cleft lip/palate, etc.)
4. Infant age ≤ 1 month
5. Mothers with pre-pregnancy body mass index $\geq 25 \text{ kg/m}^2$
6. Mothers ≥ 18 years old
7. Parental plan to exclusively feed infant 19-20 kcal/ounce formula upon delivery or by the start of the intervention period ~ 1 month after delivery
8. Parental intention to have infant well child visits through age 6 months at a Division of Academic General Pediatrics practice site (Hope Drive, Elizabethtown, Nyes Road)
9. English speaking parent

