3.2 Exclusion Criteria

Create a numbered list of the exclusion criteria that define who will be excluded in your study.

1. Infants who weigh less than their birthweight 21 days after delivery

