7.1 Study Design

Describe and explain the study design.

This study is a randomized, clinical trial involving 60 exclusively formula fed infants born at ≥ 37 weeks gestational age who are at-risk for overweight based upon maternal pre-pregnancy overweight or obesity (or alternatively at first prenatal visit if pre-pregnancy weight/height not known) and infant birthweight $\geq 50^{\text{th}}$ percentile. Infants will be enrolled at Penn State Health Children's Hospital or at affiliated clinics within the Division of Academic General Pediatrics between birth and age 1 month, where they will be randomized to a calibrated formula intake intervention or control. Participating infants in the intervention group will be seen monthly until age 6 months where they will be weighed and measured, and parents will complete surveys related to volume of formula consumed, infant appetite, parent feeding style, and infant temperament. Control infants will follow the same procedures, but will not have scheduled visits at ages 3 and 5 months. Instead their visits will correspond to usual care well child visits at ages 1, 2, 4, and 6 months.

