7.2 Study Procedures

Provide a step by step description of all research procedures being conducted (broken down by visit, if applicable) including such information as below (where and when applicable); describe the following:

- HOW: (e.g., data collection via interviews, focus groups, forms such as surveys and questionnaires, medical/school records, audio/video/digital recordings, photographs, EKG procedures, MRI, mobile devices such as electronic tablets/cell phones, observations, collection of specimens, experimental drug/device testing, manipulation of behavior/use of deception, computer games, etc.)

- WHERE: (e.g., classrooms, labs, internet/online, places of business, medical settings, public spaces, etc.)

Prior to enrollment, infants will be screened by study coordinators to ensure eligibility consistent with study inclusion/exclusion criteria.

7.2.1 Visit 1

Provide a description of what procedures will be performed on visit 1 or day 1 or pre-test in order of how these will be done. If your study only involves one session or visit, use this section only and indicate 7.2.2 as not applicable.

Birth – infant age 1 month: Parents will then review and complete the informed consent document during the birth hospitalization or at a clinic visit allowing for continued participation. Demographic data will be collected from parent-completed surveys on Redcap. Study coordinators will review the electronic medical record to obtain data related to pregnancy and birth history (e.g. birthweight, gestational age, maternal pre-pregnancy BMI, etc.). Additionally, parent contact information will be obtained.

Anthropometrics – if enrollment occurs during the birth hospitalization, birth weight and birth length will be recorded from the electronic medical record. If enrollment occurs at an outpatient clinic visit, the following procedures will be used (and for all subsequent weights and lengths):

- Weight – will be measured to the nearest 0.001 kg using a calibrated, digital electronic scale
- Recumbent Length – will be measured to the nearest 0.1 cm using a portable stadiometer (Shorr)

Diary card - Parents will be given a diary card to record volume of infant formula consumed for the 3 days prior to the 1 month well child visit (Visit 2) and all subsequent visits. Instructions for the diary card will ask parents:

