- a) Volume consumed in each feeding for the day (volume is the amount that passes the infant's lips – if formula is spit-up, it still counts as having been consumed)
- b) Type of infant formula
- c) Size of bottle used
- d) Other sources of nutrition (e.g. juice, water, foods)

Randomization – following the visit, infants will be randomized to intervention or control using a computer-generated randomization program generated by a statistician not affiliated with the trial. Randomization will include stratification for sex of the infant (male/female) and maternal pre-pregnancy BMI category ($25-29.9 \text{ kg/m}^2$ vs. $\geq 30 \text{ kg/m}^2$).

7.2.2 Visit 2

Provide a description of what procedures will be performed on visit 2 or day 2 or post-test in order of how these will be done. If your study involves more than two sessions or visits replicate this section for each additional session or visit (e.g., 7.2.3, 7.2.4, etc.).

Age 1 Month Visit (ages 24 – 41 days)

Both study groups:

1. Anthropometrics of infant (weight, recumbent length)
2. Parent-completed Surveys
 - a. Baby Eating Behavior Questionnaire⁷⁶
 - b. Babies Basic Needs Questionnaire

- c. Single item adapted from the Infant Feeding Practices Study II⁷⁷: “I encourage my infant to finish his or her bottle of formula”⁷⁸; responses include:
Never Rarely Sometimes Most of the time Always.....
- 3. Diary cards to be completed for the 3 days following the visit
- 4. Diary cards to be completed x 3 days prior to next study visit

Intervention group only:

1. Parents will be provided with handouts on hunger/satiety cues and calming a fussy baby
2. Parents will be given a digital streaming copy of the video, “Happiest Baby on the Block” available at: <https://www.happiestbaby.com/products/baby-streaming-video-english>
3. Parents will be given a copy of a video demonstrating responsive bottle feeding: <https://youtu.be/NLnPGJKdPUw>⁷⁸
4. Parents will be given a copy of Bottle Feeding Basics video: <https://360.articulate.com/review/content/99a63b9a-184c-474e-b836-7d8cd8aa1652/review>
5. Study coordinators will provide parents with a range of formula volume to be consumed based upon research conducted by Butte:⁷⁹

Table 8 Energy requirements for formula-fed infants 0–12 months of age

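### Randomisation can come before the switch to exclusive formula and the day-21 weight are known, and Visit 2 sets a sole-source formula volume without checking the switch

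*Combined protocol and SAP*

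**What the plan says.** **Feeding criterion.** Section 3.1, item 7, asks for a "Parental plan to exclusively feed infant 19-20 kcal/ounce formula upon delivery or by the start of the intervention period", put at about 1 month. It is a statement of intent, and the switch may come late. Section 7.1 describes the sample in the present tense: "This study is a randomized, clinical trial involving 60 exclusively formula fed infants".

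**Screening and randomisation.** Section 7.2 has coordinators screen eligibility once, before enrolment. Section 7.2.1 places randomisation after Visit 1, which may fall in the birth hospitalisation or at a clinic visit up to 1 month. Section 1.1 is more specific: "A cohort of 60 infants will be recruited and randomized 2-3 weeks after birth".

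**Exclusion.** The only criterion in 3.2 is "Infants who weigh less than their birthweight 21 days after delivery".

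**Visit 2 (7.2.2, ages 24-41 days).** The intervention arm gets its first formula volume here. It is built from current weight and the kcal/kg/day requirement in Table 8, which is for formula-fed infants. At WFL at or above the 75th percentile, 10% is taken off. No step confirms that formula is now the only milk, and nothing is deducted for other milk.

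**Diary.** At Visit 1 parents receive a card "to record volume of infant formula consumed for the 3 days prior to the 1 month well child visit". One of its items is "Other sources of nutrition (e.g. juice, water, foods"). No rule says that the card is read before the volume is set, or what follows if it shows other milk.

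**Withdrawal.** Section 3.3.1 covers failure-to-thrive and missed visits only. Under 3.3.2, withdrawn infants provide no further data and are not replaced.

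**The concern.** An infant should be randomised when eligibility is settled. Here two facts that bear on eligibility can still be open at that moment, and the plan does not say what to do when either turns out badly.

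The first is feeding. A volume equal to the whole energy requirement (or 90% of it) is right only if formula is the sole source of energy. If the planned switch has not happened by Visit 2, breast milk comes on top of that volume. Part or all of the extra cut is then offset, and the contrast with ad lib feeding shrinks.

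The second is the day-21 weight. An infant randomised in the third week who is then below birthweight at day 21 must either be kept although ineligible or be removed after randomisation. Removal under 3.3.2 would mean no further data and no replacement. In a trial of 60, about 30 per arm if allocation is equal (the ratio is not stated), one infant is 1/30 = 3.3% of an arm.

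**Working it through.** **1. Timing.** Inputs: randomisation at 2-3 weeks, that is days 14-21 (1.1); Visit 2 on days 24-41 (7.2.2); exclusion judged at day 21 (3.2).

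- Gap from randomisation to Visit 2: shortest 24 - 21 = 3 days, longest 41 - 14 = 27 days. The switch may legitimately fall anywhere in this gap.
- Within days 14-21, only randomisation on day 21 itself can use a day-21 weight. Days 14-20 come before it.
- Nothing differs between the arms before Visit 2. Handouts, videos and volumes all start there, so randomising earlier gains no treatment time.

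**2. The plan's own figure.** Section 7.2.2 puts the 10% cut at about 3 ounces a day. From Table 8 at 1 month, with formula at 20 or 19 kcal/oz:

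- Boys: 4.58 kg x 122 kcal/kg = 559 kcal (table 560), or 27.9-29.4 oz. Ten percent is 2.8-2.9 oz.
- Girls: 4.35 kg x 117 kcal/kg = 509 kcal (table 509), or 25.4-26.8 oz. Ten percent is 2.5-2.7 oz.

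Both round to the stated figure. The calculation also confirms that the volume covers the infant's whole requirement before the cut.

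**3. Breast milk that cancels the extra cut (WFL at or above the 75th percentile).** Let R be the requirement, b the breast-milk energy and c the fraction of b that the infant offsets by taking less formula. The documents give no value for c, so a range is assumed.

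Total intake = 0.90R + (1 - c)b. This equals R when b = 0.10R / (1 - c).

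- c = 0: 10% of R; boys 0.10 x 560 = 56 kcal/day, girls 0.10 x 509 = 51.
- c = 0.5: 20% of R; 112 and 102 kcal/day.
- c = 0.75: 40% of R; 224 and 204 kcal/day.
- c = 1: no dilution.

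At break-even the infant is back at 100% of the calibrated requirement. The extra cut is lost; the calibration is not. Below the 75th percentile there is no cut to absorb the breast milk, so any amount not offset puts intake above the calibrated requirement.

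**4. Cost in consents if randomisation waits.** Let q be the share of consented infants who have not switched by Visit 2 (assumed). Consents needed = 60 / (1 - q).

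- q = 5%: 63.2, so 64.
- q = 10%: 66.7, so 67.
- q = 20%: 75.

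Section 15.2 expects 200-300 eligible infants a year, so 100-150 in the 6-month recruitment period of 8.1. Sixty is 40-60% of that pool and 75 is 50-75%. Section 15.2 starts from infants already expected to be exclusively formula fed, at no stated age, so taking off non-switchers may partly double count.

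**The case against.** **Criterion 7 is deliberate.** It openly allows time to switch, and 1.1 defines the population by the mother's choice to formula feed. This stands. A reader might infer that the randomised cohort differs from the one in the objective; a population defined by intention does not support that. Mixed feeding before Visit 2 is no fault. The gap is only that nothing closes the switching period when the first volume is set.

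**Some materials are out of view.** Sections 4.0 and 7.0 send screening questions and data collection forms to a separate upload. The diary's list of other sources is open-ended, so it can capture breast milk, and naming breast milk is a matter of wording. This stands too. What can be judged is the protocol's procedure, and it attaches no action to the diary.

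**The volume is not a fixed dose.** Parents are told to prepare the lower end and add more only if hunger cues persist. Some compensation is therefore likely, and c = 0 is an upper bound on dilution, not a working case.

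**Timing.** Section 7.1 has infants enrolled "between birth and age 1 month, where they will be randomized to a calibrated formula intake intervention or control". A reader might infer randomisation at birth, but the age window there most naturally governs enrolment. The 2-3 weeks of 1.1 is the explicit age, and the point needs no more than that.

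**Adherence.** A reader might infer that mixed feeding spoils the adherence endpoint. That endpoint is "parent adherence to formula volume recommendations as measured by 3 day feeding diaries at 2, 3, 4, 5, and 6 months". It claims to measure adherence to formula volume, not total intake, and it does so.

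**A lighter remedy exists.** Randomisation could stay where it is, with a rule added for reading the pre-Visit-2 diary. That would catch unswitched infants, but only after they are randomised, and it would leave the day-21 problem untouched.

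**Conclusion.** The point holds as a cheap improvement. Followed as written, the plan can randomise infants before their feeding status and day-21 weight are known, and it then sets a sole-source formula volume without confirming that formula is the only milk.

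For feeding, the consequence is dilution. In an unswitched infant at WFL at or above the 75th percentile, the extra cut at 1 month is cancelled by about 51-56 kcal/day of breast milk with no compensation, and by 102-112 kcal/day if half is offset. These figures use Table 8 reference weights and assumed values of c. For the day-21 rule, the consequence is a post-randomisation exclusion or an ineligible inclusion, with no instruction on which.

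How many infants are affected cannot be derived from the documents and may be small. A reader might therefore want a dilution figure for the whole arm. None is available, because neither the share unswitched nor the share at or above the 75th percentile is given. Nor do the documents support a claim of bias in a particular direction, or of underfeeding: breast milk added to the recommended volume raises intake.

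**What to change.** Keep consent early, with the 1-month age limit (criterion 4) tied to consent. Randomise at Visit 2, before any arm-specific material is given, once:

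- the parent confirms, or the existing pre-Visit-2 diary shows, that 19-20 kcal/oz formula is now the infant's only milk; and
- the day-21 weight rule has been checked. Visit 2 starts on day 24, so the rule can be settled by then; state which weight is used.

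Align 1.1, 3.1 (item 7), 7.1 and 7.2.1 to this timing. Keep every randomised infant in follow-up and in the as-randomised analysis, including any who later receive breast milk. Report the number consented but not switched as a feasibility count under 1.3. The pilot then supplies the figure that is now missing, which is useful because 8.2 intends these data to size the next trial.

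**Cost.** One question or one look at the diary, a sentence in each of four sections, and allocation available in clinic. Both stratification factors, infant sex and maternal BMI category, are already known from Visit 1. A few more consents are needed per randomised infant: 64-75 for 60 randomised if 5-20% have not switched (assumed). At the low end of the expected pool, 75 would be tight but attainable. No intervention time is lost.
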